2.10 PD and PK/PD analyses

A scatter plot of KAF156 and lumefantrine day 8 concentrations will be produced. The dots on this plot will be colored according to the cure status (both PCR-corrected and uncorrected ACPR29), which will allow the assessment whether patients with lower concentrations have higher failure rate.

[figure not shown]
In addition, the PK and PD data obtained in the study may be pooled together with data from other studies and exploratory exposure-response modeling may be performed. An exploratory exposure-response analysis for safety outcomes such as QTc may also be conducted. These analyses may not be part of the CSR and may be reported separately.

2.11 Patient-reported outcomes

NA

2.12 Biomarkers

NA

2.14 Overview of analysis methods

An overview of statistical analyses and methods applied to efficacy variables and safety variables are given in [Table 2-4](#) and [Table 2-5](#). Descriptive statistics will be provided by cohort regardless of whether Cohort 2 stops early or not.

Table 2-4 Overview of analysis methods for baseline data and efficacy variables

Variable(s)	Summary statistics for binary/categorical data	Listings	Between treatment comparison	95% CI for each treatment group	Summary statistics for continuous data	Time-to-event data analysis K-M	Graphs	Pooled analysis (Cohort 1, 2)
Medical history	X	X	-	-	-	-	-	-
Demographics and baseline characteristics	X	X	-	-	-	-	-	X
Patient disposition	X	X	-	-	-	-	-	X
Prior medication use	X	X	-	-	-	-	-	-
Concomitant medication use	X	X	-	-	-	-	-	-
Concomitant rescue medication use	X	X	-	-	-	-	-	-
Concomitant Non-study drug antimalarial medication use	X	X	-	-	-	-	-	-
Prior other prohibited medications use	X	X	-	-	-	-	-	-
Concomitant other prohibited medications use	X	X	-	-	-	-	-	-
PCR-corrected Response at Day 29	X	X	X	X	-	X	X	X
PCR-corrected response at Days 15 and 43	X	X	X	X	-	X	X	X
Uncorrected ACPR response at Days 15, 29, and 43	X	X	X	X	-	X	X	X
Proportion of patients with parasitaemia at 12, 24, and 48 hours after treatment;	X	X		X	-	-	-	X
Time to parasite clearance (PCT)		X	X	-	-	X	X	X
Time to fever clearance (FCT)		X	X	-	-	X	X	X
Proportion of patients with early treatment failure	X	X	-	X	-	-	-	X

Variable(s)	Summary statistics for binary/ categorical data	Listings	Between treatment comparison	95% CI for each treatment group	Summary statistics for continuous data	Time-to-event data analysis K-M	Graphs	Pooled analysis (Cohort 1, 2)
Proportion of patients with late clinical failure	X	X	-	X	-	-	-	X
Proportion of patients with late parasitological failure (LPF)	X	X	-	X	-	-	-	X
Incidence rate of recrudescence at Days 15, 29 and 43	X	-	-	-	-	X	X	X
Incidence rate of reinfection at Days 15, 29 and 43	X	-	-	-	-	X	X	X
Scatter plot of KAF156 and lumefantrine day 8 concentrations with ACPR29	-	-	-	-	-	-	X	X

Table 2-5 Overview of analysis methods for safety/PK variables

Variable(s)	Summary statistics for binary/categorical data	Listings	Summary statistics for continuous data	Graphs	Pooled analysis (Cohort 1, 2)
AE	X	X	-	-	X
SAE	X	X	-	-	X
severe malaria	X	X	-	-	
Adverse events of special interest	X	X	-	-	X
Hematology change from baseline	-	X	X	X	X
Biochemistry changes from baseline	-	X	X	X	X
Liver abnormalities	X	X	-	-	X
ECG abnormality	X	X	-	-	X
QTc change from baseline	-	X	X	X	X
Vital signs change from baseline	-	X	X	-	X
Notable vital signs abnormality	X	X	-	-	X
Drug concentrations	-	X	X	X	X
PK parameters	-	X	X	-	X

2.15 Interim analysis

Safety/efficacy/PK data for each Cohort will be analyzed after first 24 patients in each Cohort. The results for the run-in cohorts will be communicated to relevant internal and external people who will contribute to the selection of effective and safe dose for next Cohort or continuation of the same Cohort. The results for Cohorts 1 and 2 will be limited to DMC only.

DMC analysis: DMC analyses will be performed at the following timepoints

- After the first 24 patients in the Run-in Cohort (12 to <18 years) have been treated and followed up for at least 2 weeks,
- After the first 24 patients in Cohort 1 (2 to <12 years) have been treated and followed up for at least 2 weeks,
- After the first 24 patients in Cohort 2 (6 months to <2 years) have been treated and followed up for at least 2 weeks. In case results (PK, safety and efficacy data) from the initial 24 patients are non-conclusive, another DMC review may be scheduled after the first 48 patients of Cohort 2 have been dosed and followed up to Day 15.
- After the Run-in Cohort is repeated for a different dose group or an earlier ad-hoc safety review is triggered in case 5 SAEs (irrespective of relationship) or 3 SAEs with a suspected relationship are reported.

The 24 patients are the targeted number in each group/cohort. The actual number may be slightly different.

Below is the outline of the data required for the DMC review in [Table 2-6](#)

Table 2-6 **Specification of data outputs for DMC data review**

Output	Analysis set	Periodic data review	
		After first 24 patients in each Cohort/group	Periodic safety data review
Baseline			
Patient disposition	Randomized	Yes	Yes
Recruitment by country and center	Randomized	Yes	Yes
Demographic characteristics	FAS	Yes	Yes
Background disease characteristics	FAS	Yes	Yes
Safety			
Concomitant medications/significant non-drug therapies	Safety	Yes	Yes
All adverse events and Serious adverse events	Safety	Yes	Yes
General, and liver, specific safety laboratories (categorical analysis)	Safety	Yes	Yes
Vital signs (clinically notable)	Safety	Yes	Yes
ECG	Safety	Yes	Yes
Early treatment failures	Safety	Yes	Yes
Efficacy			
Parasite clearance time (PCT)	FAS	Yes	As needed
PCR uncorrected ACPR at Day 15	FAS	Yes	No
PCR uncorrected ACPR at Day 29	FAS	As available*	No
PCR uncorrected ACPR at Day 43	FAS	As available*	No
KAF156 and luLumefantrine (C6hr, AUC,, AUC, H168 concentration)	PK	Yes	As needed

FAS: Full analysis set

*Data may not be available for all patients for a data/DMC review

3 Sample size calculation

3.1.1 Primary endpoint(s)

The primary objective is to evaluate the efficacy of KAF156 combined with LUM-SDF by demonstrating non-inferiority to Coartem[®] in PCR corrected ACPR at Day 29 for treatment of uncomplicated malaria caused by *P. falciparum* in children 6 months to < 12 years old. The NI margin (Δ) has been set to 10%. There is no historical Coartem[®] trial that compared Coartem[®] with placebo in PCR corrected ACPR at Day 29 to justify the NI margin statistically. The 10% NI margin in PCR corrected ACPR at Day 29 is based on clinical judgement as a NI margin of 10% to 12.5% is commonly used in other infection diseases (e.g., FDA 2018 guidance for

Complicated Urinary Tract Infections, FDA 2020 guidance for Hospital-Acquired Bacterial Pneumonia and Ventilator-Associated Bacterial Pneumonia, EMA 2014 Addendum to the guideline on the evaluation of medicinal products indicated for treatment of bacterial infections, etc.).

The statistical null hypothesis is that the difference in PCR-corrected ACPR rate at Day 29 between KAF156 and LUM-SDF combination and Coartem[®] is at most -10% with the alternative hypothesis that it is greater than -10%. The non-inferiority of KAF156 and LUM-SDF combination in PCR corrected ACPR rate at Day 29 will be evaluated based on the per-protocol analysis set using Cohorts 1 and 2 pooled if Cohort 2 does not stop early or using Cohort 1 data alone if Cohort 2 stops early.

Cohort 2 does not stop early

The statistical hypothesis will be evaluated using the lower limit of 2-sided 95% confidence interval (CI) for the difference between two treatment groups using Cohorts 1 and 2 pooled based on Mantel-Haenszel estimate of the common risk difference stratified by cohort (see [SAS manual version 13.2 Pages 2681-2682, 2014](#)). If the lower confidence limit is greater than -10%, the null hypothesis will be rejected. That means the non-inferiority will be established at -10%.

[figure not shown]
Assuming that the true response rate in PCR corrected ACPR at Day 29 is 95% for both treatment groups, a sample size of 92 patients per group will have at least 87% power to reject the null hypothesis that the response rate for KAF156 and LUM-SDF combination is at least 10% lower than Coartem[®] at 1-sided alpha of 2.5% (nQuery 8.4 module PTE0-1/Two Group Test of non-inferiority in Proportions).

Assuming that about 16% of patients will be excluded from the per-protocol analysis set, about 220 patients overall will be randomized in 1:1 to the 2 treatment groups to yield 92 evaluable patients per treatment group in pooled Cohorts 1 and 2. The number of evaluable patients in the PPS may be reduced further due to other unforeseen issues, such as COVID19. In this case, additional number of patients will be randomized to match the requirement of PPS.

Cohort 2 stops early

In case that Cohort 2 stops early after 24 patients, the statistical hypothesis will be tested using Cohort 1 data alone. Therefore, the 80 patients that are allocated to Cohort 2 will be re-allocated into Cohort 1 so that about 220 patients are randomized in Cohort 1 to achieve at least 87% power to demonstrate the non-inferiority in patients with 2 to 12 years old.

Figure 3-1 Power to reject adequate clinical and parasitological response (ACPR) rate less than or equal to 80% based on 2-sided 95% CI by true rate

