#### 12.4.2 Statistical model, hypothesis, and method of analysis

The primary objective is to demonstrate the non-inferiority (NI) of a KAF156 and LUM-SDF combination to Coartem® for treatment of uncomplicated malaria caused by *P. falciparum* in children 6 months to < 12 years old. The NI margin ( $\Delta$ ) has been set to 10%.

The statistical null hypothesis is that the difference in PCR-corrected ACPR rate at Day 29 between KAF156 and LUM-SDF combination and Coartem® is at most -10% with the alternative hypothesis that it is greater than -10%. The statistical hypothesis will be evaluated using the lower limit of two-sided confidence interval for the difference between two treatment groups.

If Cohort 2 does not stop early, two-sided 95% CI for the difference between two treatment groups will be provided for Cohorts 1 and 2 pooled using Mantel-Haenszel estimate of the common risk difference stratified by cohort (see [SAS manual version 13.2 Pages 2681-2682, 2014](#)). If the lower limit of 2-sided 95% CI for the difference is greater than -10%, the null hypothesis will be rejected.

In case that Cohort 2 stops early, such as after the first 24 patients, two-sided 95% CI for the difference between two treatment groups will be provided for Cohort 1 alone using the Wilson uncorrected method. If the lower limit of 2-sided 95% CI for the difference is greater than -10%, the null hypothesis will be rejected.

[figure not shown]
The statistical hypothesis testing will be evaluated based on the PPS.

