2.5.2 Statistical hypothesis, model, and method of analysis

The statistical null hypothesis is that the difference in PCR-corrected ACPR rate at Day 29 between KAF156 and LUM-SDF combination and Coartem[®] is at most -10% with the alternative hypothesis that it is greater than -10%. The statistical hypothesis will be evaluated using the lower limit of two-sided 95% confidence interval (CI) for the difference between two treatment groups.

If Cohort 2 does not stop early, two-sided 95% CI for the difference between two treatment groups will be provided for Cohorts 1 and 2 pooled using Mantel-Haenszel estimate of the common risk difference stratified by cohort (see [SAS manual version 13.2 Pages 2681-2682, 2014](#)). If the lower limit of 2-sided 95% CI for the difference is greater than -10%, the null hypothesis will be rejected.

In case that Cohort 2 stops early, such as after the first 24 patients, two-sided 95% CI for the difference between two treatment groups will be provided for Cohort 1 alone using the Wilson

uncorrected method. If the lower limit of 2-sided 95% CI for the difference is greater than -10%, the null hypothesis will be rejected.

The statistical hypothesis testing will be evaluated based on the PPS.

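### The power of at least 87% stated for the Cohort 1-only analysis comes from a different test; the Wilson uncorrected interval the plan specifies has about 79% with 92 evaluable patients per group

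*SAP*

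**What the plan says.** SAP 3.1.1 and Protocol 12.8.1 give one power calculation. The planning rate is 95% in each arm. On that basis, the plan states that "a sample size of 92 patients per group will have at least 87% power to reject the null hypothesis". The margin is 10%, and the calculation was run "at 1-sided alpha of 2.5% (nQuery 8.4 module PTE0-1/Two Group Test of non-inferiority in Proportions". About 16% of patients are expected to fall out of the per-protocol set (PPS), so 220 are randomized to leave 92 per group.

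The same figure is carried over to the case in which Cohort 2 stops early. The 80 Cohort 2 places move to Cohort 1 "so that about 220 patients are randomized in Cohort 1 to achieve at least 87% power". SAP 2.5 then justifies testing on Cohort 1 alone by saying that its power is sufficient, and refers back to SAP 3.1.1.

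The test itself is defined in Protocol 12.4.2 and SAP 2.5.2, on the PPS. Non-inferiority is concluded if the lower limit of a two-sided 95% interval for the difference lies above -10%. The interval depends on the branch:

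- **Cohort 2 continues:** Cohorts 1 and 2 are pooled "using Mantel-Haenszel estimate of the common risk difference stratified by cohort".
- **Cohort 2 stops early:** the interval "will be provided for Cohort 1 alone using the Wilson uncorrected method". SAP 5.7.1 gives the formula and SAP 5.7.3 the SAS option (Newcombe).

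Neither document gives a power or an error rate for either interval.

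**The concern.** The sample size rests on one test and the decision on another. With response near 95%, methods for a difference in proportions do not behave alike. A Wald-type interval is short and tends to be liberal, while the Wilson-based interval is pulled away from 100% and is more cautious. A power computed for a Wald-type test need not hold for a Wilson-based rule.

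If it does not hold, the early-stop branch is weaker than the plan tells its readers, and SAP 2.5 leans on that strength. The opposite question arises for the pooled branch: whether its Wald-type interval holds the stated 2.5% one-sided error.

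**Working it through.** **Inputs.** From SAP 3.1.1: 95% response in both groups, 10% margin, one-sided alpha 2.5%, 92 evaluable per group, 220 randomized, 16% excluded. From Protocol section 3: 140 patients in Cohort 1 and 80 in Cohort 2.

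**1. The plan's own figure.** Evaluable per group: 220 × 0.84 / 2 = 92.4. With the unpooled normal approximation, SE = √(2 × 0.95 × 0.05 / 92) = 0.03213. Power = Φ(0.10 / 0.03213 − 1.96) = Φ(1.152) = 87.5%. The stated 87% is reproduced.

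**2. Cohort 1 alone, Wilson uncorrected.** The lower limit is d − √{(p₁ − l₁)² + (u₂ − p₂)²}, where l₁ is the lower Wilson limit for KAF156/LUM-SDF and u₂ the upper Wilson limit for Coartem. I summed the binomial probabilities of all 93 × 93 outcomes for which this limit exceeds -10%.

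| Evaluable per group | Power at 95% vs 95% |
|---|---|
| 90 | 79.4% |
| 92 | 78.9% |
| 93 | 80.2% |
| 94 | 81.7% |
| 100 | 83.2% |
| 110 | 87.1% |

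The values around 92 show that the shortfall does not come from the discreteness of one sample size. Power first passes 87% at 110 per group. At 16% exclusion that is 220 / 0.84 ≈ 262 randomized. One-sided error at 92 per group (85% vs 95%) is 2.4%, so this interval holds its level.

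An example shows the mechanism. Take 85/92 responders on KAF156/LUM-SDF and 87/92 on Coartem, so d = −0.0217.

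- Wilson: l₁ = 0.8512 and u₂ = 0.9766. The lower limit is −0.0217 − √(0.0727² + 0.0309²) = −0.1008, so non-inferiority fails.
- Wald: SE = 0.0364. The lower limit is −0.0217 − 1.96 × 0.0364 = −0.0930, so non-inferiority is concluded.

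**3. Pooled analysis, Mantel-Haenszel.** Evaluable per group by cohort: 140 × 0.84 / 2 = 58.8 and 80 × 0.84 / 2 = 33.6. I took 59 + 33 = 92, with the same response rate in both cohorts (an assumption). The estimate is Σwₕdₕ / Σwₕ with wₕ = n₁ₕn₀ₕ / Nₕ, and the variance is Sato's. The four binomials were enumerated. A second split (59 + 34 vs 58 + 33) shows the sensitivity to stratum sizes.

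| Quantity | 59+33 per group | 59+34 vs 58+33 |
|---|---|---|
| Power, 95% vs 95% | 86.1% | 87.2% |
| One-sided error, 80% vs 90% | 2.8% | 2.7% |
| One-sided error, 85% vs 95% | 3.4% | 3.3% |
| One-sided error, 88% vs 98% | 3.9% | 4.3% |
| One-sided error, 89% vs 99% | 4.4% | 5.4% |

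A stratified Newcombe interval with Mantel-Haenszel weights holds the error at about 2.3% to 2.5% for 85% vs 95%, with power of about 80% (78.5% to 80.2% over the constructions and splits tried).

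**The case against.** The strongest reply is that the early-stop branch is a contingency, that its Wilson interval controls the false-positive rate, and that the shortfall harms only the sponsor's chance of success. That is correct. Restating the figure changes no decision rule. Power is also sensitive to the assumed response: the Wilson rule at 92 per group has 84.4% power if both groups are at 96%, and 90.4% at 97%. But the plan assumes 95%, and at 95% its figure does not hold.

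The provision to randomize more patients if exclusions run high does not close the gap, because it restores only the PPS requirement, which is 92 per group. Nor does the ceiling of 268 for Cohorts 1 and 2. It is 220 plus up to 48 Cohort 2 patients, and those patients do not enter the test.

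A reader might infer more than the documents support:

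- **That 87% power fails in both branches.** It does not. Pooled power is 86% to 87%.
- **That false positives run at nearly twice nominal.** The 4.4% figure (4.4 / 2.5 ≈ 1.8) needs a Coartem rate of 99%, which appears nowhere in the documents, and it moves with a patient or two in the stratum sizes. At the planned 95% the ratio is about 1.3.
- **That the 87% is an arithmetic slip.** It follows correctly from its formula. The formula does not match the analysis.
- **That the choice of branch lets the result be steered.** The branch follows a Data Monitoring Committee (DMC) review of the dose in Cohort 2, and both intervals are fixed in advance.

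The Mantel-Haenszel interval is pre-specified in both documents. Replacing it would cost about 6 points of pooled power, a trade-off on which a sponsor could reasonably differ.

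**Conclusion.** The concern holds for the Cohort 1-only branch. Under the plan's own assumptions (95% in both groups, 10% margin, 92 evaluable per group), the specified interval gives about 79% power, some 8 points below the stated minimum. The type II risk is 21%. The reliance in SAP 2.5 on adequate power in that branch inherits the error.

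The secondary point is smaller and separate. The pooled test has the power stated, but at a one-sided error of about 3.3% to 3.4% for a 95% Coartem rate, not 2.5%. Values of about 4% to 5% apply only if Coartem were at 98% to 99%, which is an assumption. All pooled figures assume equal response rates and equal exclusion in the two cohorts.

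**What to change.** 1. In SAP 3.1.1 and Protocol 12.8.1, restate the Cohort 1-only power as about 79% with 92 evaluable per group, and name the interval it refers to. If 87% is to be kept for that branch, the plan must provide for about 110 evaluable per group (about 262 randomized).
2. In SAP 2.5, replace the statement that Cohort 1 alone is sufficiently powered with the corrected figure.
3. In SAP 3.1.1, state that the pooled Mantel-Haenszel interval has a one-sided error of about 3.3% to 3.4% at the planned Coartem rate, and how this changes with that rate.
4. In SAP 2.5.4, add a stratified score-type interval, such as the stratified Newcombe, as a sensitivity analysis of the pooled primary comparison.

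Replacing the primary pooled interval is left to the sponsor. It would also require changes to Protocol 12.4.2 and 12.8.1 and an entry in SAP section 4, and would lower pooled power to about 80%.

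Items 1 to 4 cost text changes before database lock and one added analysis. No patients are added, unless the sponsor chooses to restore 87% in the early-stop branch. The price is a less favourable stated power.

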3.1.2 Secondary endpoint(s)

Run-in Cohort

The main objective in the Run-in Cohort is to investigate the food effect in terms of fold increase in exposure for fed vs fasted. The sample size will be justified based on the precision for estimating the fold increase in LUM exposure for fed vs fasted. The fold increase will be estimated using the geometric mean ratio between fed and fasted groups with the precision defined by the half-width of 90% confidence interval for the geometric mean ratio.

It is well known that the distribution of PK parameters, such as AUC or Cmax, is best described by log normal distribution. The geometric mean ratio along with its 90% confidence interval will be calculated first using log value and then anti-log transformed to ratio. The relevant historical data for sample size calculation are the standard deviations of log values. In the phase

2 study CKAF156A2202 Part A, the standard deviations from sparse PK samples of lumefantrine for KAF156 400 mg/LUM-SDF 960 mg QD 2 days (under fasted) were:

- 0.69 for log C_{max} of last dose
- 0.77 for log AUC_{0-24h} of last dose
- 0.63 for log concentration at 168 hours.

For log C_{max}, assuming that the common standard deviation is 0.69, a sample size of 8 patients per group will provide an 80% probability that the half-width of 2-sided 90% confidence interval for the difference of two log means will be ≤ 0.693 or 2 in terms of ratio (nQuery MTC1-1). The probability will be increased to 90% if the sample size is 9 patients per group.

For log AUC_{0-24h}, assuming that the common standard deviation is 0.77, a sample size of 10 patients per group will provide an 80% probability that the half-width of 2-sided 90% confidence interval for the difference of two log means will be ≤ 0.693 or 2 in terms of ratio (nQuery MTC1-1).

For log concentration at 168 hours, the required sample size is smaller for the same half-width and probability since its standard deviation is smaller.

Considering that about 20% of patients may be excluded from PK analysis, 24 patients will be randomized in the Run-in Cohort to yield about 9 to 10 evaluable for the analysis of the above LUM PK parameters.

Power consideration for PK checking after the first 24 patients in Cohort 2

After about 24 patients have been randomized in Cohort 2, PK checking along with safety and efficacy will be evaluated to see if the dose level of KAF156 and/or LUM-SDF is appropriate for this age group. Since lower lumefantrine concentration at 168 hours is associated with higher recrudescence in Coartem[®] ([WWARN Lumefantrine PK/PD Study Group, 2015](#)), lumefantrine concentration at 168 hours will be the key PK parameter to be checked. Difference in lumefantrine concentration at 168 hours between the 2 treatment groups (KAF156 and LUM-SDF combination divided by Coartem[®]) will be evaluated using the geometric mean ratio and its 90% confidence interval between the 2 groups. In the KAF156A2202 Part A, the SD of log lumefantrine concentration at 168 hours was 0.63 and 0.51 for KAF156 400 mg/LUM-SDF 960 mg QDx2 group and Coartem[®], respectively. Therefore, it's assumed that the common SD for KAF156 and LUM-SDF combination and Coartem[®] in this study is 0.57 (average of 0.63 and 0.51). Assuming that there is no difference in lumefantrine concentration at 168 hours between the two treatment groups, a sample size of 10 patients per group will provide 80% power to reject the null hypothesis that the lumefantrine concentration at 168 hours is at least 50% lower in the KAF156 and LUM-SDF group than in the Coartem[®] group at 1-sided alpha of 5% (nQuery 8.4 Module MTE0-1/Two Group t-test of Non-Inferiority in Means). To adjust for potential non-evaluable lumefantrine concentration at 168 hours, the PK checking will be performed after approximately 24 patients have been randomized and reached the visit at Day 8.

Power consideration for safety (QTcF effect) in the first 24 patients in Run-in Cohort

Mean and median max QTcF changes from baseline were similar between the POC study KAF156X2201 with KAF156 alone and KAF156A2202 Part 'A' with LUM-SDF (internal data), which indicated that lumefantrine may not contribute to additional QTcF changes when in combination with KAF156. Therefore, we hypothesized that increase in lumefantrine exposure under fed condition may not further increase QTcF. The purpose of QTcF checking for the first 24 patients in the Run-in cohort is to ensure that there is no unacceptable increase in QTcF with food intake. A QTc increase of > 20 ms for a drug compared to placebo is listed as a serious concern in ICH E14 (2005). Hence, a NI margin of 20 ms is selected for comparing the 2 treatment groups in QTcF changes for the first 24 patients in the cohort. Considering that about 15% patients may not be evaluable for QTc change, about 10 patients per treatment group will be considered for the power calculation. In CKAF156A2202 study, the SD for maximum change from baseline to any post baseline was about 20 ms in the 8 arms. Assuming a SD of 20 ms and there is no difference in QTcF change between the 2 treatment groups, there is an 80% power to show that the treatment group with fed does not increase QTcF more than 20 ms compared to the treatment group under fasting using 2-sided 80% confidence interval (i.e., the upper limit of 2-sided 80% confidence limit for the difference between two treatment groups (fed Vs fasted) in mean maximum QTcF change is less than 20 ms) (nQuery Advisor 7.0 module MTE0-1).

4 Change to protocol specified analyses

None

5 Appendix

